5.2 Study Population

Patients who meet all the inclusion and none of the exclusion criteria will be enrolled in the RCT part of the study.

Inclusion Criteria

- PE with severe features, diagnosed using the ACOG standard criteria⁴ requiring magnesium sulfate
- Females older than 18 years of age
- Singleton pregnancy
- Gestational age greater than 24 0/7 weeks
- The patient is physically and mentally able to understand the informed consent and is willing to participate in this study
- Able to speak English or Spanish

Clinical Protocol: Cheetah® OSU study

Exclusion Criteria

- Multiple gestation
- Prisoners
- Patients with chronic renal insufficiency or epilepsy
- Known cardiovascular disease
- Patients with contraindications to magnesium sulfate use (e.g. myasthenia gravis)
- Patients with eclampsia or HELLP syndrome
- Contraindications for magnesium sulfate

5.3 Study Outcomes

Primary Outcome:

Duration of magnesium sulfate use in the postpartum period defined as the duration in hours between delivery and discontinuation of magnesium sulfate.

Secondary safety Outcome:

Composite of eclampsia, pulmonary edema, renal insufficiency/acute kidney injury, venous thromboembolism, peripartum cardiomyopathy, ICU admission, or maternal death.

Secondary Maternal clinical Outcomes

Maternal secondary outcomes

- Need for or up-titration of antihypertensive agents postpartum for severe hypertension
- Hospital readmission up to 4 weeks postpartum
- Changes in arterial blood pressure in the peripartum period
- Changes in cardiac output during the peripartum period
- Changes in heart rate in the peripartum period
- Need to restart magnesium sulfate
- Urine output, and the onset of diuresis defined as UOP >0.5ml/hour for 2 consecutive hours
- Preeclampsia symptoms resolution
- Correlation between magnesium levels and changes patient hemodynamics
- Anesthetic type
- Length of stay in Labor and delivery
- Total hospital length of stay
- Hospital cost
- Patient satisfaction

Clinical Protocol: Cheetah® OSU study

- Time to start regular diet and ambulation
- Maternal non-invasive cardiac parameters pre- and post-neuraxial anesthesia, pre- and post starting magnesium sulfate, with pushing or during cesarean delivery, and after the use of different anti-hypertensives (e.g. labetalol, nifedipine, hydralazine) for emergent therapy for severe hypertension
- Postpartum hemorrhage or blood transfusion
- Postpartum resources utilization including ER/triage visits, scheduled or non-scheduled clinic visits

Neonatal secondary outcomes

- Fetal or neonatal death
- Intubation, continuous positive airway pressure (CPAP) or high-flow nasal cannula (HFNC) for ventilation or cardiopulmonary resuscitation within first 72 hours
- Composite of either neonatal encephalopathy as defined by the NICHD Neonatal Research Network criteria, seizures, or intracranial hemorrhage (intraventricular hemorrhage, subgaleal hematoma, subdural hematoma, or subarachnoid hematoma)
- Hyperbilirubinemia requiring phototherapy or exchange transfusion
- Hypoglycemia (glucose < 35 mg/dl) requiring IV therapy
- NICU admission and length of stay in NICU

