Moreover, there is no consensus in the published trials regarding the optimal dose to use (both loading and maintenance), or the duration of therapy (especially in the postpartum period) ⁴. Multiple recent studies have questioned the utility of the use of magnesium sulfate for 24 hours postpartum and suggest no increased risk of eclampsia or maternal morbidity with use of shorter durations of use (such as 6 hours or 12 hours)¹²⁻¹⁴. However, most studies have no clear definition of a clinical parameter that defines the recovery phase from severe PE. One of several parameters that has been described as an indicator of clinical improvement from PE is the onset of diuresis¹⁵. This is believed to be a signal for reversal of increased SVR (vasoconstriction), and thus resolution of the disease. Historically, it was only possible to measure SVR with an invasive monitor such as a pulmonary artery catheter. The potential complications with these measurements outweighed the risk of benefit. Novel techniques including thoracic bioreactance, enable minimally invasive measurements of SVR and have been validated in the obstetric population.¹⁶

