5.4 Study Procedures

Patients with PE with severe features admitted for delivery, will be screened for eligibility. Those who meet all the inclusion criteria and none of the exclusion criteria will be approached for participation. Subjects shall sign an informed consent form (ICF) approved by our site's Institutional Review Board (IRB), which includes Health Information Portability and Accountability Act (HIPAA) authorization information. The informed consent process shall be completed by the PI or designee prior to initiation of the study procedures. The original signed and dated informed consent form is to remain in the subject's research records; one copy is provided to the subject; and per site requirements, once copy placed in the medical record.

If a patient expressed interest and signs the ICF, she would be enrolled in the study and randomized to one of the two arms. Randomization will occur as soon as decision to deliver is made, and before start of mgSO4. Those assigned to the Cheetah arm, will have the device placed ASAP after randomization and before start of magnesium sulfate, in order to obtain baseline hemodynamic parameters.

In addition to subjects enrolled in the RCT, we propose an optional negative control cohort of 25 normotensive healthy women delivering > 37 weeks to compare hemodynamics.

Once informed consent is obtained, baseline procedures including collection of demographic, medical and obstetric histories, vitals (weight, height, and blood pressure), concomitant medications (con meds), and other pertinent clinical information will be obtained. Intrapartum and postpartum outcomes, including receipt of anesthesia and anti-hypertensive medications will be collected. In addition to collecting non-invasive cardiac parameters, hourly urine output and serial magnesium sulfate levels will be measured. Delivery outcomes (maternal and neonatal clinical information) will be collected on all subjects enrolled in the study.

Clinical Protocol: Cheetah® OSU study

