7.2.4 Primary efficacy analysis

The primary outcome will be compared between the two study arms using either a 2-sample t-test or the Wilcoxon Rank Sum test, depending on the distribution of the data. Multivariate linear regression modeling adjusting for race, gestational weeks, body mass index (BMI, continuous), and other significant variables will provide the primary efficacy analysis for this study. All other analyses are considered exploratory.

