7.2.5 Sample size assessment and feasibility

Assuming an average reduction in magnesium sulfate use of 4 hours in the Cheetah® device group, alpha error of 5% and power of 90%, the study requires 21 patients in each arm. Allowing for 15% drop out, we plan to enroll a total of 60 patients.

In addition to subjects enrolled in the RCT, we propose an optional negative control cohort of 25 normotensive healthy women delivering > 37 weeks to compare hemodynamics.

The OSUWMC is a tertiary care referral center for the central Ohio region, with a delivery volume more than 5200 patients per year. In addition, we receive close to 750 transfers per year for high risk conditions including preeclampsia. The total number of women admitted with preeclampsia yearly is more than 450 patients. Given the high prevalence of preeclampsia with severe features at our tertiary care center, we anticipate completion of enrollment within 1 year.

Clinical Protocol: Cheetah® OSU study

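### Onset of diuresis is defined by a urine output above 0.5 ml/hour, a threshold nearly every woman passes in the first two hours, so the outcome cannot separate patients or arms

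*Combined protocol and SAP*

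**What the plan says.** Among the maternal secondary outcomes, section 5.3 lists "Urine output, and the onset of diuresis defined as UOP >0.5ml/hour for 2 consecutive hours". The threshold is an absolute hourly volume, and no other section defines, qualifies or repeats it.

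Section 3.2 explains why the event is of interest: "One of several parameters that has been described as an indicator of clinical improvement from PE is the onset of diuresis". It adds that diuresis is thought to reflect reversal of the raised SVR, and so resolution of the disease.

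On data, section 5.4 states that "hourly urine output and serial magnesium sulfate levels will be measured", and it includes weight among the baseline vitals. The eligibility criteria in section 5.2 exclude "Patients with chronic renal insufficiency or epilepsy". Section 7.2.4 makes the adjusted regression on magnesium duration the primary efficacy analysis and says of the rest: "All other analyses are considered exploratory".

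**The concern.** A definition of onset must be capable of failing. Some women should not have met it at the first reading, so that the time at which they do meet it carries information. A threshold of 0.5 ml/hour is close to no urine at all. Almost any woman with measurable urine flow passes it in the first two hourly readings, and her recorded onset time is then simply the earliest time the schedule allows.

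The stated objective is to show that a fall in SVR indicates resolution of preeclampsia. Onset of diuresis is a recovery sign that the protocol itself ties to SVR. It can be observed in both arms, whereas section 5.4 describes placing the device only in the Cheetah arm. If onset time hardly varies, it cannot correlate with the time of the SVR fall and cannot differ between arms. There is also a risk of misreading: a comparison showing no difference could be reported as similar recovery when the definition allowed no other result.

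**Working it through.** The threshold is a definition, so there is no derived figure in the plan to reproduce. The check is unit arithmetic, followed by an illustration under stated assumptions.

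**Inputs from the documents**
- Threshold: more than 0.5 ml/hour in each of 2 consecutive hours (5.3).
- Urine output measured hourly; weight taken at baseline (5.4).
- Planned enrolment: 60 women (7.2.5).

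**Assumptions (not in the documents)**
- Body weights of 60 to 100 kg for the main comparison, 50 to 120 kg as a wider range.
- Hourly urine output log-normal, median M from 10 to 100 ml/hour, log-scale standard deviation s from 0.5 to 1.0, the two hours independent. If the hours are positively correlated, the chance that both exceed the threshold is higher, so independence does not favour the concern.

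**Step 1: the literal threshold**
- Over two hours: 0.5 × 2 = 1 ml.
- Over a day: 0.5 × 24 = 12 ml.

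**Step 2: chance of meeting the written rule in a given pair of hours**

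q = 1 − Φ((ln 0.5 − ln M)/s), and the chance that both hours exceed the threshold is q².

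- Worst case tried, M = 10 and s = 1.0: (ln 0.5 − ln 10)/1.0 = −3.00, q = 0.9986, q² = 0.9973. Among 60 women, 60 × 0.0027 = 0.16 would be expected to miss the rule in that pair of hours; the chance that all 60 meet it is about 0.85.
- M = 30 and s = 1.0: q² = 0.99996, and the chance that all 60 meet it is 0.9975.
- Every other setting with M of 30 or more gives at least 0.9999.

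Under the written rule, onset therefore falls in the first assessable two-hour window for essentially all women.

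**Step 3: what a per-kg reading would mean (illustration only)**

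Cutoff = 0.5 × weight.

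| Weight (kg) | Cutoff (ml/hour) | Multiple of written cutoff |
|---|---|---|
| 50 | 25 | 50 |
| 60 | 30 | 60 |
| 80 | 40 | 80 |
| 100 | 50 | 100 |
| 120 | 60 | 120 |

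**Step 4: would such a cutoff vary between women?**

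The same formula with 40 ml/hour (80 kg) in place of 0.5 gives, over s = 0.5 to 1.0:

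| Median M (ml/hour) | Chance that both hours exceed 40 ml |
|---|---|
| 10 | under 1% |
| 30 | 8% to 15% |
| 50 | 35% to 45% |
| 100 | 67% to 93% |

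A cutoff of that order separates low from high output over the range tried; the written one does not. This does not show that 0.5 ml/kg/hour is the right marker of diuresis. It shows only that the denominator decides whether the outcome carries information.

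**The case against.** The strongest reply is that this is an obvious slip in one part of one exploratory outcome. Several parts of that reply stand:

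- The same bullet also lists urine output itself, which is unaffected and can still be compared between arms and over time.
- Other recovery measures in section 5.3 are intact, including symptom resolution, blood pressure changes, up-titration of antihypertensives and restarting of magnesium.
- The threshold does not enter the primary outcome, the SVR stopping rule, the safety composite or the sample size.
- The plan nowhere specifies an analysis of diuresis onset against SVR. Using it as a check on the SVR marker is an inference from section 3.2. Because diuresis is believed to follow from the fall in SVR, it is not a wholly independent check.
- The per-kg reading, the weight range and the urine-output distribution are all assumptions, and the plan does not say when the clock for onset starts.

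None of this rescues the written cutoff, which is too low to mark diuresis across the whole range tried. Nor does an obvious slip correct itself. The documents do not state the intended unit, and leaving the analyst to choose one after the data are in would make the definition post hoc.

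**Conclusion.** The concern holds. As written, the rule detects that urine flow is not absent. It does not detect onset of diuresis, and it would give a near-constant onset time in both arms.

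The 12 ml/day figure is pure arithmetic on the written threshold. The figure of at least 99.7% rests on the assumed output distributions, and the multiple of 60 to 100 rests on a per-kg intention and weights of 60 to 100 kg. A dropped weight term is the likely cause, but the documents do not confirm it.

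The consequence is limited to the onset component of an exploratory secondary outcome. The sponsor should correct it, but the trial's main comparison does not depend on it.

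**What to change.** Amend the definition in section 5.3 before any data are analysed. State the threshold with its denominator, either per kg per hour using the baseline weight or as an absolute hourly volume. The sponsor should supply the value and confirm that it marks onset of diuresis, not merely the absence of anuria. The same line should say from which time point onset is counted. Then derive onset from the recorded hourly urine output.

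The cost is one line of text. Hourly output and weight are already to be collected, so no new measurement is needed, and any readings already taken can be used under the corrected definition.

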5.4 Study Procedures

Patients with PE with severe features admitted for delivery, will be screened for eligibility. Those who meet all the inclusion criteria and none of the exclusion criteria will be approached for participation. Subjects shall sign an informed consent form (ICF) approved by our site's Institutional Review Board (IRB), which includes Health Information Portability and Accountability Act (HIPAA) authorization information. The informed consent process shall be completed by the PI or designee prior to initiation of the study procedures. The original signed and dated informed consent form is to remain in the subject's research records; one copy is provided to the subject; and per site requirements, once copy placed in the medical record.

If a patient expressed interest and signs the ICF, she would be enrolled in the study and randomized to one of the two arms. Randomization will occur as soon as decision to deliver is made, and before start of mgSO4. Those assigned to the Cheetah arm, will have the device placed ASAP after randomization and before start of magnesium sulfate, in order to obtain baseline hemodynamic parameters.

In addition to subjects enrolled in the RCT, we propose an optional negative control cohort of 25 normotensive healthy women delivering > 37 weeks to compare hemodynamics.

Once informed consent is obtained, baseline procedures including collection of demographic, medical and obstetric histories, vitals (weight, height, and blood pressure), concomitant medications (con meds), and other pertinent clinical information will be obtained. Intrapartum and postpartum outcomes, including receipt of anesthesia and anti-hypertensive medications will be collected. In addition to collecting non-invasive cardiac parameters, hourly urine output and serial magnesium sulfate levels will be measured. Delivery outcomes (maternal and neonatal clinical information) will be collected on all subjects enrolled in the study.

Clinical Protocol: Cheetah® OSU study

5.5 Data Collection

Case Report Forms (CRFs) will be completed by research staff through patient interview and medical chart abstraction. Clinical data, including subject demographics and information on the current and previous pregnancies, The PI or designated staff reviews CRFs and database entry for accuracy.

Information obtained directly (patient interview) or indirectly (chart abstraction) is specifically for research purposes and obtained by trained members of the site's research staff. No subject names or other identifiers will be recorded on CRFs. Paper CRFs will be utilized with data written legibly, using black pen. Source documents will be kept as originals in the site's specific research chart. All entries will be signed and dated. Corrections will be made by making a single strike through on the prior entry with correction to the side to include date and in the initials of the research staff. Research staff will undergo an initiation training session to learn standard procedures for data entry.

5.6 Subject's Study Duration

In addition to the immediate delivery and postpartum data collection, postpartum data including any readmissions, ER/triage visits, scheduled or non-scheduled clinic visits will be recorded up to 4 weeks postpartum. If patient did not present for follow up, a phone call will be made to collect these data. Therefore, participation in this study ends after the last contact with the patient with a maximum potential study duration would be 4 weeks.

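### The only planned follow-up call goes to women who did not attend, so a woman seen early in the 4-week window has no planned later contact, and events at other hospitals after that visit can be missed.

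*Combined protocol and SAP*

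**What the plan says.** Section 5.3 lists among the maternal secondary outcomes "Hospital readmission up to 4 weeks postpartum" and "Postpartum resources utilization including ER/triage visits, scheduled or non-scheduled clinic visits". The safety composite in the same section has no stated time window.

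Section 5.6 sets the collection window: readmissions, ER/triage visits and "scheduled or non-scheduled clinic visits will be recorded up to 4 weeks postpartum". It then gives the one active step for obtaining these data: "If patient did not present for follow up, a phone call will be made to collect these data". It closes by saying that "participation in this study ends after the last contact with the patient with a maximum potential study duration would be 4 weeks".

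Section 5.5 names the data sources: "Case Report Forms (CRFs) will be completed by research staff through patient interview and medical chart abstraction". No request for records from other hospitals is described. No study visit at or near week 4 is scheduled, and the term follow-up is not tied to any particular visit or day.

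**The concern.** The outcome window is the same for every woman, but the planned contact is not. The call is triggered by non-attendance, so attending a visit, even an early one, can remove the only prompt for asking about the rest of the window. From then on, an event is captured only if it appears in the site's own chart. An admission or ER visit at another hospital may not.

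The hypothesis in section 4 has two parts: a shorter infusion, and no rise in maternal morbidity. Readmission and ER/triage use bear on the second part. So might late composite events, if the composite is meant to extend past discharge. With about 30 women per arm, event counts will probably be small, so one or two unrecorded events would matter to how the morbidity results read.

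Clinic visits are also a listed outcome. One outcome would then help to decide how long the others are actively observed. The arms differ visibly (device-guided stopping against a fixed 24 hours) and no blinding is described, so attendance could differ between them.

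**Working it through.** The plan states no figure on this point, so there is none to reproduce. The check is a reading of the text, followed by an illustration on stated assumptions.

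**Step 1. Apply the text to a woman seen once, on day d, with d well before day 28.**
- Window for her events: delivery to 4 weeks, or 28 days (5.3, 5.6).
- Call: not triggered, because she presented for follow-up (5.6).
- Later study visit: none scheduled.
- End of participation: can be day d, since 4 weeks is only a maximum (5.6).
- Sources after day d: chart abstraction only, because no further interview is planned (5.5).

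The exposure is limited to events that occur after day d, at another hospital, and that do not reach the site chart.

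**Step 2. Share of the window without planned contact.** The formula is (28 − d)/28. The day d is an assumption, because the documents give none.
- d = 7: 21/28 = 75%
- d = 10: 18/28 = 64%
- d = 14: 14/28 = 50%
- d = 21: 7/28 = 25%

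**Step 3. Possible number of missed events.** Only the 60 women come from the documents (7.2.5). The following are assumptions: an event risk r of 5–10%, events spread evenly over 28 days, a share s of 20–50% occurring elsewhere and never reaching the site chart, and every woman last seen on day 7–14.
- Expected events: 60 × r = 3 to 6.
- Missed events: 60 × r × s × (28 − d)/28.
- Low end: 60 × 0.05 × 0.2 × 0.50 = 0.3.
- High end: 60 × 0.10 × 0.5 × 0.75 = 2.25, or about 2.3.

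Under these assumptions, about 0.3 to 2.3 events are missed out of 3 to 6, across both arms together.

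**Step 4. Effect on the comparison.** Let an arm's true risk be p and its missed fraction m, so that its observed risk is p(1 − m).
- Equal m in both arms: the risk difference shrinks by the factor (1 − m), and the risk ratio does not change.
- Unequal m: the observed ratio is the true ratio multiplied by (1 − m₁)/(1 − m₂), which can lie on either side of 1.

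The documents give no basis for saying which case applies.

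**The case against.** The strongest reply is that section 5.6 first commits to recording these events for all women over 4 weeks. The call can then be read as a fallback for whenever a visit has not supplied the data. Staff are not barred from calling a woman who attended, and if follow-up was meant as a visit at about 4 weeks, the gap narrows. That reading is possible, but the section does not state it. Followed literally, it plans no later contact for a woman seen early.

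Four stronger readings are tempting, and the documents do not support them.
- **That later outside events are missed.** They can be missed. Some may reach the site chart, and those before the visit can be asked about at that visit.
- **That women who miss follow-up are observed for longer than those who attend.** The call has no stated day. A woman who missed a day-10 visit could be called on day 11 and be observed no longer than an attender.
- **That the comparison is biased toward no difference.** This is not established. Equal loss leaves the risk ratio unchanged, and unequal loss can act in either direction.
- **That the referral volume shows many participants will return to other hospitals.** Section 7.2.5 says "we receive close to 750 transfers per year for high risk conditions including preeclampsia", which covers all high-risk conditions and not the 60 women randomized. Section 5.4 also places randomization before magnesium starts, so a woman transferred with magnesium already running would not fit that step. The figure makes outside care plausible and no more.

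It also stands that section 7.2.4 labels everything beyond the primary efficacy analysis exploratory, and that a pilot of 60 women could not settle rare morbidity even with complete ascertainment.

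**Conclusion.** The point holds as a gap in planned ascertainment. Section 5.6 makes its only call conditional on non-attendance, dates neither visit nor call, and lets participation end at the last contact. A woman seen early therefore has no planned later contact, and subsequent events at other hospitals can go unrecorded. Ascertainment may depend on attendance, with unknown direction between arms.

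The reach is limited to 4-week readmission, ER/triage use and possibly late composite events, the last being an inference because the composite has no stated window. Magnesium duration is unaffected.

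The size cannot be fixed from the documents. The shares of the window in the working depend on an assumed day of last contact, and the range of 0.3 to 2.3 missed events rests entirely on assumed event risk, timing and outside-care share. It shows that the loss could range from negligible to material against a small event count, and should not be quoted as an estimate. The change is worth making because it is cheap and has to be in place before follow-up closes.

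**What to change.** In section 5.6, replace the conditional call with one contact for every randomized woman in both arms, at or just after day 28 postpartum, whether or not she attended a visit. Use the same short set of questions in both arms on readmission, ER/triage visits and composite events at any hospital. Define end of participation as that contact, adjust the 4-week maximum to allow for it, and record its date. In section 5.3, count these events from delivery to day 28 for all women.

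The cost is a wording change and at most about 60 short calls by research staff who already make some of them, plus a few extra contact attempts per woman. Treatment, eligibility and sample size do not change.
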